3.0 Background For Primary Objective

3.1 Measuring Acute Toxicity

The Cancer Therapy Evaluation Program (CTEP), National Cancer Institute (NCI) Common Toxicity Criteria (CTC) was developed in 1982 for use in adverse drug experience reporting, study AE summaries, Investigational New Drug (IND) reports to the Food and Drug Administration (FDA), and publications. The CTCAE v4.0 is the first uniform and comprehensive dictionary of AE grading criteria available for use by all modalities used in the treatment of cancer. A grading (severity) scale is provided for each AE term.

The terms considered in this trial are specific to radiation toxicity and include fatigue, radiation dermatitis and brachial plexopathy. This information will be collected by the treating physician using a specific tracking form (see appendix 3). Acute Toxicity will be scored using the CTCAE v4.0 (see Appendix 1).

4.0 Correlative Studies Background

4.1 Quality of Life Assessment

Patients' quality of life assessments will be performed at regular intervals (baseline, last week of radiation treatment, 45-60 days from starting radiotherapy and 2-year follow-up). QOL will be evaluated in several ways.

First, cosmetic results will be examined using the Breast Cancer Treatment Outcome Scale (BCTOS) using patient self-reports. This brief self-report instrument has high reliability and validity, and has been used in a variety of previous studies on recovery from breast cancer treatment. [14] The BCTOS also will be used as a primary measure to assess breast-related symptoms and treatment effects. Specifically, the BCTOS will be augmented with a brief set of additional items that focus on radiotherapy-relevant symptoms (e.g., reports of skin problems, tenderness/pain in the breast, and hardness in the breast due to enhanced fibrosis). Second, we will use the MOS SF-36 Vitality Scale, a widely used measure with high reliability and validity, will assess fatigue. [15-16]

4.2 Measuring The Late Toxicities Of Breast Radiation

Radiation-induced breast fibrosis is another important late effect of radiotherapy with a commonly reported incidence of 5-15% [17-18]. Manifestations of radiation-induced breast fibrosis include pain, cosmetic deformities, and diminished quality of life. Clinically, radiation-induced breast fibrosis is characterized by skin retraction, atrophy, toughness to palpation, and decreased tissue compliance with associated functional limitations. Visual assessment and palpation are the most important clinical investigations of the skin in radiotherapy but they

are subjective and unquantitative.

Hoeller et al. recently reported a careful comparison of The Radiation Therapy Oncology Group (RTOG) and Late Effects Normal Tissue Task Force subjective, objective, management, and analytic (LENT/SOMA) scores for late breast toxicity after radiation in a group of breast cancer patients. [19] In comparison, when LENT/SOMA criteria were used, telangiectasia and pigmentation were upgraded in 34% and 36%, respectively, and telangiectasia was downgraded in 45%. Inter-observer variability was similar for both classification systems and ranged from Cohen's kappa 0.3 (retraction) to 0.91 (telangiectasia). The authors concluded that LENT/SOMA criteria seem to be the better in grading and recording late radiation toxicity compared with the RTOG scale. Specifically, fibrosis scores correlated well with the LENT/SOMA scoring system (Spearman's rho 0.78, $p = 0.01$).

Brachial plexopathy is a potential toxicity associated with nodal irradiation. This side effect can significantly impair arm/shoulder function and worsen quality of life due to pain and paresthesia. Early trials of hypofractionated nodal irradiation conducted in Australia and Sweden in the 1960s revealed a 73% and 63% rate of neuropathy, respectively. However, the Australian regimen consisted of 63 Gy delivered in 12 fractions while the Swedish trial used 44 Gy in 11 fractions. Decades of experience have improved our understanding of the relationships between the volume of a critical structure treated, dose, fractionation and subsequent brachial plexus injury. We will also report this adverse effect using the LENT/SOMA scoring system.

4.3 Genetics Of Radiation-Induced Breast Fibrosis

Since the most likely long-term toxicity of accelerated radiation is soft tissue fibrosis and skin telangiectasia the preliminary recognition of genetic predispositions to these complications enables the exclusion of high-risk carriers from the trials of accelerated/hypo-fractionated radiation. In other words, similar to the impact of pharmacogenomics in medical oncology, the field of radiation-genomics is also rapidly emerging, permitting to identify individuals with genetic predisposition to inferior repair of the damage caused by ionizing radiation.

A recent study from Quarmby et al has shed some light on the genetic risk of developing breast fibrosis post-ionizing radiation. To investigate whether single nucleotide polymorphisms (SNP) of transforming growth factor beta-1 (TGF-beta1) were associated with the susceptibility of breast cancer patients to severe radiation-induced normal tissue damage Quarmby et al performed Polymerase Chain Reaction-Restriction Fragment Length Polymorphism- (PCR-RFLP) assays for TGF-beta1 gene polymorphisms on DNA obtained from 103 breast cancer patients who received radiotherapy. [21] The G-800A, C-509T, T+869C and G+915C polymorphic sites were examined, and genotype and allele frequencies of two subgroups of patients were calculated and compared. The investigators found that the less prevalent -509T and +869C alleles were significantly associated with a subgroup of patients who developed severe radiation-induced normal tissue fibrosis ($n=15$) when compared with those who did not ($n=88$) (odds ratio=3.4, $p=0.0036$, and 2.37, $p=0.035$, respectively). Furthermore, patients with the -509TT or +869CC genotypes were between seven and 15 times more likely to develop severe fibrosis. These findings imply a role for the -509T and +869C alleles in the biological mechanisms underlying susceptibility to radiation-induced fibrosis.

4.4 Blood Collection For Genomic Studies

The purpose of this portion of the study will be to collect blood from each subject accrued to the study and willing to donate a specimen of blood for research, to study the – 509C□T and +869T□C TGF- β 1 polymorphisms that have been reported to be correlated with the development of fibrosis following radiotherapy for treatment of breast cancer. [21]

For the purpose of this trial blood will be collected to enable genomic analysis for this polymorphism to explore association with the incidence of grade 3 and 4 late complications at 3 years follow up. Results of the blood test will be de-identified and will not be part of the patient's care. It will not be included in the medical record, but it will be maintained at the research office of the Department of Radiation Oncology at WCMC. When the study information is disclosed outside of WCMC as part of the research, the information that can identify the patient will be removed and the patient's records will be assigned a unique number. WCMC will not disclose the code key, except as required by law.

5.0 Patient Eligibility

5.1 Inclusion Criteria

- 5.1.1** Age older than 18
- 5.1.2** Pre- or post-menopausal women with Stage I-III breast cancer
- 5.1.3** Status post neoadjuvant systemic therapy
- 5.1.4** Status post-chemotherapy breast surgery
- 5.1.5** Original biopsy-proven invasive breast cancer, excised with negative margins of at least 1 mm (patients with focally positive margin are not excluded).
- 5.1.6** Status post segmental mastectomy or mastectomy, with either negative sentinel node biopsy and/or axillary node dissection (at least 6 nodes removed).
- 5.1.7** Patient needs to be able to understand and demonstrate willingness to sign a written informed consent document

5.2 Exclusion Criteria

- 5.2.1** Previous radiation therapy to the ipsilateral breast and/or nodal area
- 5.2.2** Active connective tissue disorders, such as lupus or scleroderma requiring flare therapy
- 5.2.3** Pregnant or lactating women
- 5.2.4** Concurrent chemotherapy, with the exception of anti HER2neu therapies
- 5.2.5** Inadequate axillary dissection in a setting of positive sentinel node
- 5.2.6** Patients with more than 5 nodes involved at axillary dissection will be excluded from this study since they will be eligible to receive radiotherapy to level I and II axilla.

6.0 Registration Procedures

6.1 General Guidelines

Patients will have completed breast cancer surgery prior to accrual into this protocol in order to establish eligibility criteria. Final pathology margins must be at least 1 mm in all directions to be eligible. The patient may undergo re-excision if the initial margins are involved or close (<

1 mm).

AJCC staging criteria will be used to identify original Clinical Stage of breast cancer patients eligible to this study. All eligible women who are referred to the Radiation Oncology Department at Weill Cornell Medicine for radiation following neo-adjuvant systemic therapy and surgery for breast cancer will be offered the opportunity to participate in this experimental protocol.

6.2 Registration Process

Before any protocol specific procedures can be carried out, investigators/staff will fully explain the details of the protocol, the study procedures and the aspects of patient privacy regarding research information. Patients will be provided a comprehensive explanation of the proposed treatment including the type of therapy, the rationale for treatment on the protocol, alternative treatments that are available, any known adverse events, the investigational nature of the study and the potential risks and benefits of the treatment. The Informed Consent document will meet all requirements of the Institutional Review Board. All subjects/patients are informed in the Consent that participation or refusal to participate in the research study will not affect any of the clinical treatment or services to which they would otherwise be entitled.

The physicians who may obtain informed consent are listed on the title page of this protocol. The Informed Consent form will be signed by the participant and the registering physician. Once signed, a copy will be given to the patient and one will be maintained with the patient's medical record. Once eligibility is confirmed and Informed Consent is documented, the patient will be registered by the study coordinator/data manager.

6.3 Randomization Process

This study is a Phase I-II non-randomized trial. Patients will be registered within 2 cohorts defined by requirement for nodal radiation (yes =Cohort 2/no= Cohort 1).

7.0 Treatment Plan

7.1 General Concomitant Medication and Supportive Care Guidelines

During radiation treatment, all patients will be prescribed daily application of Calendula lotion, to prevent skin dryness and reduce erythema.

7.2 Duration of Therapy

The treatment will consist of 15 fractions, Monday to Friday, for 3 weeks total time (over a total of 19-21 days, depending on the start day), see study calendar in Section 13.

7.3 Duration of Follow Up

Patients will be seen for follow-up at day 45-60 and then yearly thereafter for 5 years, see study calendar in Section 13.

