1.0 OBJECTIVES

1.1 Primary Objectives

- 1.1.1. To test feasibility of accelerated radiotherapy in the post-operative setting of breast cancer patients treated by neo-adjuvant chemotherapy and surgery, by evaluating the proportion of patients who experience grade II-III dermatitis within 60 days of the end of treatment.

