13.0 Study Calendar

Study	Pre Treatment	Weekly	Last week	Post Treatment (day 45-60)	Post Treatment (once/year)
History & Physical	X				
Toxicity evaluation	X	X		X	X
CBC with differential	X	X			
Comprehensive metabolic	X	as clinically indicated			
Mammogram and/or breast MRI ^a	X				X
Lumpectomy pathology report	X				
BREAST-focused exam, KPS	X	X		X	X
Blood for TGF-BETA polymorphisms	X		X ^b		
Quality of Life Questionnaires ^c	X		X	X	X
LENT/SOMA assessment					X ^c

- a. Standard mammogram or MRI for both breasts.
- b. Last day of treatment, after last dose of radiation
- c. QOL will be assessed using the Breast Cancer Treatment Outcome Scale (BCTOS) [30] MOS SF- 36 Vitality Scale (see appendix 4) at baseline, last week of radiation treatment, 45-60 days from starting radiotherapy and 2 year follow-up.
- d. Patients will be seen after completion of treatment (at day 45-60) and then yearly for five years to assess long term sequelae by LENT/SOMA scale.

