16.1 Endpoints

16.1.1 Primary endpoint

The primary endpoint for the study is acute toxicity occurring within 60 days after treatment; the proportion of patients with grade II or III acute skin toxicity.

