16.6 Statistical Analysis

16.6.1 Primary Endpoint

The primary endpoint is the occurrence of grade II or greater dermatitis within 60 days of the end of the treatment. The proportion of patients who experience this grade II or greater dermatitis will be estimated with exact 95% confidence intervals.

Patient demographic and disease characteristics at registration will be summarized using frequency distributions for qualitative data and summary statistics (means, medians, standard deviations, etc.) and graphical displays (e.g., Boxplots). Treatment data will be summarized similarly. Descriptive analyses will report the primary endpoint in subgroups defined by radiation regimen and other characteristics.

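### The first skin assessment after radiotherapy is dated differently across the protocol, and the calendar leaves 45-60 days without scheduled grading inside the primary endpoint's 60-day window

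*Combined protocol and SAP*

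**What the plan says.** **Endpoint window.** Section 16.6.1 states: "The primary endpoint is the occurrence of grade II or greater dermatitis within 60 days of the end of the treatment". Sections 1.1 ("grade II-III dermatitis within 60 days of the end of treatment") and 16.1.1 ("acute toxicity occurring within 60 days after treatment") use the same 60 days, counted from the end of treatment.

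**Toxicity schedule.** Section 10.1 sends acute and late toxicity reporting to the Study Calendar. The calendar (13.0) has toxicity evaluation weekly on treatment, then in a day 45-60 post-treatment column, then yearly. Note d reads "Patients will be seen after completion of treatment (at day 45-60", followed by yearly visits. Section 7.3 gives the same days without saying what they are counted from: "Patients will be seen for follow-up at day 45-60 and then yearly thereafter for 5 years".

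**Places that differ.**
- The Protocol Summary (Study Duration) has patients followed at 3 months after completion and then yearly.
- The Treatment Schema table has a Months 3 follow-up column, although the text above that table mentions a 45-60 day follow-up for quality of life.
- The Appendix 2 toxicity form has boxes for the three treatment weeks, 1 month and 3 months. It has no day 45-60 box.
- For quality of life only, note c of the calendar counts "45-60 days from starting radiotherapy and 2 year follow-up"; Section 4.1 and Appendix 3.2 do the same. That assessment shares the calendar column with the toxicity evaluation.

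**Duration of treatment.** Section 7.2 gives 15 fractions "over a total of 19-21 days, depending on the start day".

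**The concern.** Two things look wrong. First, the passages cannot all be followed. A first follow-up at 3 months falls outside the endpoint window, and the form used to grade the endpoint does not match the calendar that schedules it.

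Second, the calendar has no skin grading between the last weekly check and day 45-60. Section 2.2, describing an earlier series with the same breast and boost dose, says dermatitis tended to occur in the week after treatment ended. The Appendix 2 form grades what is seen at the visit and does not ask about the interval since the last one. Section 16.6.1 does not say whether dermatitis entered as an adverse event counts towards the endpoint.

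At stake is the observed event proportion in each 37-patient cohort. Missed events can only lower it, which favours concluding that the regimen is feasible.

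**Working it through.** **1. Visit dates against the 60-day window (days after the last fraction)**

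| Source | Timing | Inside 60 days? |
|---|---|---|
| Study Calendar, note d | 45-60 | yes |
| Section 7.3 | 45-60, no anchor | yes on either anchor |
| Appendix 2, first box | about 30 (1 month) | yes, but not in the calendar |
| Protocol Summary, Schema table, Appendix 2 second box | about 91 (3 months) | no; about 91 - 60 = 31 days late |

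The time after the last fraction with no scheduled skin grading is therefore 45-60 days under the calendar, or about 30 days if the form's 1-month entry is used.

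The quality of life assessment is counted from the start. With the last fraction on day 19-21, it falls between 45 - 21 = 24 and 60 - 19 = 41 days after the last fraction.

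**2. Could the questionnaire fill the gap?** The follow-up form asks about moist or raw skin over the past four weeks (28 days).
- If it is completed 45-60 days after the end of treatment, the look-back begins 45 - 28 = 17 to 60 - 28 = 32 days after the last fraction, so it misses the first week.
- If it is completed 45-60 days from the start, the look-back begins on day 17-32 of the course. That is from 17 - 21 = -4 to 32 - 19 = +13 days relative to the last fraction, so it covers that week for some patients only.

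In either case it is patient-reported and carries no toxicity grade.

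**3. What the earlier series supports.** Section 2.2, Table 1: 38 + 9 + 2 = 49 dermatitis cases among 90 patients. Grade 1 made up 38/49 = 78%. Grade 2-3 made up 11/90 = 12.2%. The statement about timing covers all grades together.

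**4. Effect on the decision rule (Section 16.3: n = 37, reject 25% at 15 or more events, alternative 25 + 18 = 43%).** The plan's own figure comes first. The exact binomial P(X ≥ 15 | 37, 0.43) is 0.678, not the stated 80%; P(X ≥ 15 | 37, 0.25) is 0.027. That power shortfall is a separate matter and does not bear on this point, but 0.678 is the correct baseline for what follows.

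The documents do not give the share of events missed. For illustration only, let the recorded rate be the true rate × (1 - share missed), with a true rate of 43%:

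| Assumed share missed | Recorded rate | P(X ≥ 15) |
|---|---|---|
| 0% | 0.430 | 0.68 |
| 10% | 0.387 | 0.47 |
| 20% | 0.344 | 0.27 |
| 30% | 0.301 | 0.12 |

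In counts, the expected number at 43% is 37 × 0.43 = 15.9. If 16 events occur and 14 are recorded, the rule is no longer met. The planned exact (Clopper-Pearson) 95% interval moves from 27.1-60.5% (16/37 = 43.2%) to 22.5-55.2% (14/37 = 37.8%), so its lower limit falls below 25%.

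At the earlier rates in the documents, with nothing missed, P(X ≥ 15) is 1.3 × 10⁻⁵ at 12.2% (Section 2.2), 1.8 × 10⁻⁶ at 10.4% and 7.0 × 10⁻⁸ at 8.1% (both Section 2.4, grade 2 or higher acute toxicity). Missing events there changes nothing.

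**The case against.** The strongest reply is that the operative schedule for toxicity is clear. Section 10.1 points to the calendar, Section 7.3 defers to it, and note d ties day 45-60 to completion, inside the window. The Protocol Summary says only that patients are followed. The schema table shows no toxicity grading at any time, even during treatment. Adverse events are recorded throughout participation, related ones are followed to resolution (10.1), and patients held for dermatitis above grade 2 are monitored until it resolves (15.2).

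Much of this stands, and it rules out several stronger readings that a reader might infer:

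- **That skin grading itself has two anchors, giving a 24-41 day gap.** The count from the start of treatment is written only for quality of life. It matters because the two assessments share a calendar column and nothing says whether they are one visit.
- **That the calendar leaves a gap of about 90 days.** That figure comes from the Summary and the schema table, not the calendar. Only a site that followed those and ignored 7.3, 10.1, 13.0 and the form's 1-month box would lack a scheduled grading inside the window.
- **That events will be lost.** The documents give no healing time for grade 2 or higher reactions, and Section 2.2 describes mostly grade 1 cases. Reactions that appear during treatment are covered by the weekly checks.
- **That the trial's conclusion is likely to change.** The missed shares are assumed, the 16-to-14 example is chosen to show where the threshold lies, and the earlier rates are far below it.

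What the reply does not remove is that the texts still disagree, the form does not match the calendar, no passage schedules skin grading in the 45-60 days after treatment, and 16.6.1 is silent on adverse event entries.

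**Conclusion.** The timing conflict is established with high confidence: the current text gives day 45-60, 3 months, and 1 and 3 months for post-treatment follow-up, and the 3-month version falls outside the endpoint window. Under-counting of the primary endpoint is a moderate-confidence risk of unknown size. It rests on Section 2.2's timing statement applying to some grade 2 or higher reactions, on some of these resolving before the visit, and on adverse event recording either not picking them up or not feeding the endpoint.

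The direction is certain, since any loss lowers the observed rate. It could alter the 15-of-37 decision only if the true rate is near the 43% alternative. At 8-12% it does not matter. Because Section 2.5 and the synopsis present the setting after neo-adjuvant therapy as untested, the low earlier rates cannot simply be assumed. This should be fixed, but it does not invalidate the design.

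**What to change.** 1. **Reconcile five places:** the Protocol Summary, the Treatment Schema, 7.3, 13.0 and Appendix 2. Count post-treatment toxicity assessments from the last fraction, with at least one inside the 60-day window. Add the day 45-60 time point to the Appendix 2 form, keep its 1-month entry and show that entry in the calendar. Aligning the form to day 45-60 alone would delete the only early grading point. State whether the quality of life assessment at day 45-60 is the same visit.
2. **Record and use the worst grade.** Add a field to the Appendix 2 form for the worst dermatitis grade since the previous assessment. In 16.6.1, derive the primary endpoint from the worst grade recorded from the start of radiotherapy through day 60 after the last fraction, including dermatitis recorded as an adverse event.

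**Cost.** Wording in five places, one added time point and one added field on the form, and one sentence in 16.6.1. Where the 1-month entry is not now being completed, scheduling it means an additional contact. Recalled severity is less exact than examination. The recorded rate may be slightly higher and less comparable with the earlier series. If accrual is under way, patients assessed before and after the change should be identified, because ascertainment would differ within a 37-patient cohort.

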7.4 Alternatives

At the time of study accrual, all patients will be offered access to the standard six weeks of radiotherapy.

7.5 Compensation

No compensation is available for participating in the study.

8.0 Surgery

Patients will have completed all surgical procedures related to breast cancer surgery prior to accrual into this protocol in order to establish eligibility criteria. Final pathology margins must be at least 1 mm in all directions to be eligible. The patient may undergo re-excision if the initial margins are involved or close (< 1mm). If the patient meets the eligibility criteria after re-excision, she may be entered onto the study. Patients undergoing reconstructive surgery are eligible either after maximum expansion of tissue expanders or after completion of breast reconstruction.

While currently women with a variety of clinical presentations of breast cancer are offered a neo-adjuvant systemic approach (stage I-III), eligibility to this protocol will require assessment of nodal status at surgery, either by sentinel node and/or axillary dissection (minimum 6 nodes).

